6.3.1.1 Dose Modification Rules for Transient Post-Infusion Hyperglycemia

Patients who develop transient post-infusion glucose >250 mg/dL after study drug administration may continue treatment. However, the next infusion must be delayed until the patient's pre-infusion glucose levels return to <160 mg/dL (fasting) or <200 mg/dL (non-fasting). Guidelines for the management of transient glucose increases are given in the tables below. The continuing occurrence of post-infusion blood glucose >500 mg/dL, based on repeated laboratory analysis despite optimal glucose-lowering therapy after 2 infusions of copanlisib, will require dose reduction by one dose level.

- Further dose reduction (where appropriate per study design/population) is allowed as long as discontinuation criteria were not met.
- Dose re-escalation is allowed when a patient has achieved controlled glucose levels per investigator's judgment.

Proprietary Information of MD Anderson

Protocol 2020-1241

19 October 2022

- Persistent occurrence of post-infusion blood glucose >500 mg/dL based on laboratory analysis, which occurred at the lowest dose level despite optimal glucose-lowering therapy (after at least one cycle of treatment) with the consultation of a diabetes specialist requires permanent discontinuation of the study drug.

Table 9: Management of post-infusion glucose increase

Toxicity	Action to be Taken
Glucose increase of CTCAE Grade 1 (abnormal glucose level above baseline with no medical intervention)	
• Continue study treatment
Glucose increase of CTCAE Grade 2 (change in daily management, from baseline for a diabetic; oral antiglycemic agent is initiated; workup for diabetes)	
• Hydration as clinically indicated• When planning next infusion prophylaxis with oral glucose-lowering medication per local SOC is recommended• Consultation with an endocrinologist for diabetic patients is recommended
Glucose increase of CTCAE ≥Grade 3 (insulin therapy initiated; hospitalization or urgent intervention indicated; life-threatening consequences)	
• Hydration as clinically indicated (orally, IV)• Insulin therapy per local SOC• When planning next infusion consider prophylaxis with oral glucose-lowering medication per local SOC• Consultation with an endocrinologist is recommended

Table 10: Management of Transient Glucose Increase on the Day of Copanlisib Infusion

Criteria	Recommendations
Asymptomatic glucose increases to a value ≤250 mg/dL	
• Does not generally require treatment with glucose-lowering medication.
Asymptomatic glucose increases to a value >250 mg/dL	
• Should have repeated laboratory glucose determination.• If the repeated glucose value is decreasing, the glucose may be followed without glucose-lowering medication treatment if hydration status is normal as clinically assessed.• Consultation with an endocrinologist is recommended.• Hydration, if appropriate.

Proprietary Information of MD Anderson

Protocol 2020-1241

19 October 2022

	
When planning the next infusion, consider prophylaxis with oral glucose-lowering medication.
Symptomatic or persisting glucose increases to a value >250 mg/dL	
Hydration status should be clinically assessed.If the clinical assessment is consistent with dehydration, fluids should be given as clinically appropriate (orally or IV).Laboratory tests confirming increase should be repeated. If the repeated glucose value is persistent and/or the patient is symptomatic and/or the hydration status indicates the need for hydration, glucose-lowering medication should be administered.Prompt input from a diabetes specialist should be obtained.Hydration if appropriateRapid/short-acting insulin may be given for glucose persisting at >250 mg/dL or if the patient is symptomatic during the infusion day.Rapid/short-acting insulin.According to the institution sliding scale coverage of glucose persisting at >250 mg/dL is recommended, with oral or IV hydration as clinically appropriate. When planning the next infusion, consider prophylaxis with oral glucose-lowering medication.

Table 11: Management of Transient Glucose Increase on Subsequent Days Following Copanlisib Infusion

Criteria	Recommendations
Grade 2 Max post infusion glucose >200 mg/dL noted on subsequent days	
Oral glucose-lowering medication recommended on subsequent days.Consultation with an endocrinologist is recommended.The use of sulphonylurea/metaglinides, insulin

Proprietary Information of MD Anderson

Protocol 2020-1241

19 October 2022

	
secretagogues medications to manage increased glucose levels post drug infusions is not recommended.
 
• Treatment with glucose-lowering medication suggested according to the local standards of practice.•
--	---

The need for glucose monitoring at home should be determined by the investigator based on the post-infusion glucose profile and clinical status of the patient.

6.3.1.2 Monitoring of diabetic patients

If the patient already monitors his/her blood glucose as part of routine anti-diabetic care, the routine measurements should not be replaced by the study-specific measurements.

6.3.1.3 Management of Blood Pressure Increases Associated with Copanlisib

It is important that patients with pre-existing arterial hypertension adhere to their regular medication schedule and take their usual doses on the days of study drug infusion.

The management of acute BP increases following copanlisib will need to be individualized for each patient, but experience from a Bayer-sponsored phase 1 study with copanlisib has suggested the benefit of dihydropyridine calcium channel blockers (i.e., amlodipine, felodipine). Topical nitrates should also be considered. Verapamil and diltiazem (non-dihydropyridine calcium channel blockers and moderate inhibitors of CYP3A4) should be used with caution due to a potential CYP3A4 interaction. In general, it is advisable for investigative teams to be prepared, so that anti-hypertensive medication is readily available in case of need.

In the event of the occurrence of arterial hypertension $\geq 150/90$ mmHg during infusion of copanlisib at any cycle, antihypertensive treatment is suggested as indicated in the Dose Modification of Copanlisib for Arterial Hypertension **Table 13** below. In the event of the occurrence of grade 3 arterial hypertension ($\geq 160/100$ mmHg) during infusion of copanlisib, the infusion should be interrupted, and anti-hypertensive treatment, as suggested above, is administered. The infusion can be resumed when BP has returned to $< 150/90$ mmHg.

Table 12: Management of Blood Pressure

Toxicity (CTCAE)	Study Drug action	Recommendation
Pre-dose measurements BP $\geq 150/90$ mmHg	No dose should be given until recovery to $< 150/90$ mmHg	Consider BP-lowering medication. Dosing can proceed on the scheduled day if, after at least 2 consecutive measurements, BP returns to

Proprietary Information of MD Anderson

Protocol 2020-1241

19 October 2022

		<150/90 mmHg. If BP doesn't return to <150/90 mmHg, delay dosing until the next visit.
During infusion: CTCAE hypertension of grade 3 or $\geq 160/100$ mmHg	The infusion can be interrupted or slowed down, and the administration of BP-lowering therapy should be initiated.	The infusion may be resumed when BP has returned to <150/90 mmHg at the investigator's discretion or skipped. Subsequent study drug administrations may be reduced by 1 dose level at the investigator's discretion ^a .
Post-dose: Drug-related CTCAE hypertension of grade 3 or $\geq 160/100$ mmHg ^b		Administration of BP-lowering therapy should be initiated according to the local SOC. Additional measurements to be performed as clinically indicated until recovery to <150/90 mmHg. Subsequent study drug administrations may be reduced by 1 dose level at the investigator's discretion ^b .
CTCAE hypertension of grade 4	Permanent discontinuation	

^a: The lowest dose level is 45 mg.
^b: Not manageable despite optimal antihypertensive treatment.

6.3.1.3.1 Blood pressure measurement on treatment days

BP will be measured every 5-10 minutes prior to each copanlisib dose (no more than 4 measurements) until there are two consecutive results <150/90 mmHg. If BP is $\geq 150/90$ mmHg, the investigator can consider a medical intervention or delaying the infusion of the study drug. The patient should rest for 5-10 min before BP is recorded.

On infusion days, BP will be measured at 0 hour (pre-dose), 30 minutes (mid-infusion), 60 minutes (end of infusion), and 1 hour after the end of infusion

Proprietary Information of MD Anderson

Protocol 2020-1241

19 October 2022

NOTE: A window of ± 10 minutes is allowed for all BP measurements, except for pre-dose (0 hour) measurement.

6.3.1.4 Dermatologic toxicity

The recommendations for dose modifications in cases of dermatologic toxicity are outlined in **Table 14**. If these recommendations are not followed, the rationale for other measures will be documented in detail in the participant's medical record.

Table 13: Dose modification of copanlisib for dermatologic toxicity

Toxicity (CTCAE grade)	Occurrence	For current course of therapy	For next course of therapy
Grade 1 and 2	Any appearance	No change	No change
Grade 3 ^a	1 st appearance	Interruption until Grade ≤ 2	Decrease by one dose level ^b
	2 nd appearance	Interruption until Grade ≤ 2	Decrease by one dose level ^b
	3 rd appearance	Permanent discontinuation	—
Grade 4	1 st appearance	Permanent discontinuation	—

Abbr.: CTCAE = Common terminology criteria of adverse events.

a. Despite maximum supportive therapy.

b. The lowest dose level is 30 mg; if a participant is already on the 30 mg dose level study intervention and meets criteria for further decrease of dose, copanlisib will be discontinued permanently.

If dermatologic changes occur, the participant should be treated quickly and aggressively. **Table 15** can be used as guidance.

Proprietary Information of MD Anderson

Protocol 2020-1241

19 October 2022

Table 14: Guidance on treatment of skin toxicities

MILD (CTCAE Grade 1)	
Dry Skin /	Emollients, - Eucerin or Aquaphor plus gentle soaps
Fissures	(Dove, Cetaphil, Basis), use fragrance free detergents
Rash	Topical hydrocortisone 2.5% and/or clindamycin 1% gel plus doxycycline 100 mg b.i.d. or Minocycline 100 mg b.i.d.
Nail Changes	Moisturizers
Pruritus	Pramoxine 1% cream or Sarna Ultra Cream
MODERATE (CTCAE Grade 2)	
Dry Skin /	Emollients and topical as above plus Ammonium lactate or Urea 20%
Fissures	
Rash	Topical hydrocortisone 2.5% and/or clindamycin 1% gel plus doxycycline 100 mg b.i.d. or Minocycline 100 mg b.i.d.
Nail Changes	Vinegar soaks (dilute 1:1 white vinegar in water and soak fingers for 10 min a day)
Pruritus	H1-anti-histamines
SEVERE (CTCAE Grade 3 or 4)	
Dry Skin /	As above for Moderate
Fissures	
Rash	As above for Moderate plus Medrol dose pack
Nail Changes	Topical antibacterial / antifungal (ciclopirox) cream or Topical high potency steroids (clobetasol ointment) Consider dermatology consult for nail avulsion
Pruritus	Pregabalin 50-100 mg b.i.d.

Abbr.: b.i.d. = Twice daily, CTCAE = Common terminology criteria for adverse events.

6.3.1.5 Management of Infections

Serious, including fatal, infections occurred in 8.9% of 558 patients treated with copanlisib monotherapy. The most common serious infection was pneumonia. Monitor patients for signs and symptoms of infection and withhold copanlisib for Grade 3 and higher infection.

Serious pneumocystis jiroveci pneumonia (PJP) occurred in 0.9% of 558 patients treated with copanlisib monotherapy. Before initiating treatment with copanlisib, consider PJP prophylaxis for populations at risk. Withhold copanlisib in patients with suspected PJP infection of any grade. If confirmed, treat infection until resolution, then resume copanlisib at previous dose with concomitant PJP prophylaxis

6.3.1.6 Management of Non-Infectious Pneumonitis

The investigator is requested to differentiate between non-infectious pneumonitis, and infectious pneumonitis (viral, bacterial, or fungal), aspiration pneumonitis, or other pneumonitis clearly not due to a potential hypersensitivity reaction to the copanlisib infusion; and provide the

Proprietary Information of MD Anderson

Protocol 2020-1241

19 October 2022

basis for his/her assessment that it is infectious or other, as appropriate. The investigator is requested to report with the most specific clinical terms to describe the condition, not simple “pneumonitis”.

In the event of suspected non-infectious pneumonitis, modify copanlisib treatment as per **Table 16** below.

Table 15: Management of Non-Infectious Pneumonitis

Suspected or confirmed NIP per CTCAE	Action taken	Re-treatment dose after recovery
Grade 1	No Change	N/A
Grade 2	Dose Interruption Until recovery to ≤Grade 1	Decrease dose to the next lowest dose level ^a .
Grade 2 second re-occurrence	Permanent Discontinuation	N/A
Grade 3	Permanent discontinuation	N/A
Grade 4	Permanent discontinuation	N/A

NA = Not applicable; NIP = Non-infectious pneumonitis;
^a: Not applicable for 45 mg dose level. No re-escalation is allowed after the dose reduction. The lowest dose level is 45 mg; if a patient is already on the 45 mg dose level and cannot tolerate treatment study treatment will be discontinued permanently.

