6.3.1 Copanlisib toxicity management

Table 5: Management of Nausea/vomiting

Toxicity	Action to be Taken
CTCAE Grade 1	No change in dose
CTCAE Grade 2	Hold* until \leq Grade 1. No change in dose
CTCAE Grade 3	Hold* until \leq Grade 2. Resume at one dose level lower, if indicated.**
CTCAE Grade 4	Off copanlisib treatment

*Patients requiring a delay of >2 weeks may go off protocol therapy.
**Patients requiring >2 dose reductions should go off protocol therapy.

Recommended management: Antiemetics

Table 6: Management of Diarrhea

Toxicity	Action to be Taken
CTCAE Grade 1	No change in dose
CTCAE Grade 2	Hold* until \leq Grade 1. No change in dose
CTCAE Grade 3	Hold* until \leq Grade 2. Resume at one dose level lower, if indicated.**
CTCAE Grade 4	Off copanlisib treatment

*Patients requiring a delay of >2 weeks may go off protocol therapy.
**Patients requiring >2 dose reductions should go off protocol therapy.

Proprietary Information of MD Anderson

Protocol 2020-1241

19 October 2022

Recommended management: Loperamide antidiarrheal therapy

Dosage schedule: 4 mg at the first onset, followed by 2 mg with each loose motion until diarrhea-free for 12 hours (maximum dosage: 16 mg/24 hours)

Adjunct anti-diarrheal therapy is permitted and should be recorded when used.

Table 7: Management of thrombocytopenia

Toxicity	Action to be Taken
CTCAE Grade 1	No change in dose
CTCAE Grade 2	No change in dose
CTCAE Grade 3	Hold* until \leq Grade 1. Resume at one dose level lower, if indicated. **
CTCAE Grade 4	Off copanlisib treatment

*Patients requiring a delay of >2 weeks may go off protocol therapy.

**Patients requiring >2 dose reductions should go off protocol therapy.

Table 8: Management of Neutropenia

Toxicity	Action to be Taken
CTCAE Grade 1	No change in dose
CTCAE Grade 2	No change in dose
CTCAE Grade 3	Hold* until \leq Grade 2. Resume at one dose level lower, if indicated. **
CTCAE Grade 4	Off copanlisib treatment

*Patients requiring a delay of >2 weeks may go off protocol therapy.

**Patients requiring >2 dose reductions should go off protocol therapy.

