6.3.3 Other toxicities

Other toxicities that are not clearly attributable to copanlisib or fulvestrant, including overlapping toxicities, should be initially managed as follows:

- Treatment interruption or dose modification for Grade 1 or grade 2 AEs per CTCAE would be implemented at the investigator and patient's discretion.
- Both agents should be interrupted for Grade 3 AEs per CTCAE until the AEs have reached grade 1 or have returned to baseline. Following the resolution of toxicity, copanlisib may be resumed at the same dose level or at one or more dose levels lower, at the investigator's discretion. Fulvestrant should be resumed at the same dose level. Sequential reintroduction of each agent should be considered if clinically appropriate.
- Both agents should be interrupted for Grade 4 AEs per CTCAE until the AEs have reached grade 1 or have returned to baseline. For AEs that are not life-threatening and that can

Proprietary Information of MD Anderson

Protocol 2020-1241

19 October 2022

be managed, treatment with copanlisib may be resumed at a lower dose level, but fulvestrant should be resumed at the same dose level. Otherwise, patients must discontinue treatment. Sequential reintroduction of each agent should be considered if clinically appropriate.

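### Two copanlisib footnotes put the lowest dose level at 45 mg and a third puts it at 30 mg, and none is limited to one toxicity

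*Combined protocol and SAP*

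**What the plan says.** Tables are cited here by their captions; some cross-references in the text run one number higher.

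- **Starting dose.** Section 2.1 and note j of Appendix A give copanlisib 60 mg on Days 1, 8 and 15 of each 28-day cycle.
- **Blood pressure (section 6.3.1.3, Table 12, footnote a).** "The lowest dose level is 45 mg".
- **Skin toxicity (section 6.3.1.4, Table 13, footnote b).** "The lowest dose level is 30 mg; if a participant is already on the 30 mg dose level study intervention". A patient at that level who meets the criteria for another decrease comes off copanlisib permanently. The table steps the dose down one level at the first Grade 3 appearance, one more at the second, and stops at the third.
- **Pneumonitis (section 6.3.1.6, Table 15, footnote a).** "The lowest dose level is 45 mg; if a patient is already on the 45 mg dose level"; a patient there who cannot tolerate treatment is stopped permanently. The Grade 2 row reads "Decrease dose to the next lowest dose level", and the footnote adds the exemption "Not applicable for 45 mg dose level".
- **Glucose (section 6.3.1.1).** Continuing post-infusion glucose above 500 mg/dL leads to a one-level reduction, and further reductions are allowed where appropriate. Permanent discontinuation follows persistent values above 500 mg/dL "which occurred at the lowest dose level despite optimal glucose-lowering therapy". The section names no dose in mg.

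**The concern.** The footnotes describe one drug with one starting dose, and each states its floor as a plain fact about the dose levels. An investigator with a patient at 45 mg needs to know whether 30 mg exists. The protocol answers yes in one table and no in two others. The answer decides between continued treatment at a lower dose and permanent withdrawal of copanlisib. It also feeds the dose reductions and toxicity-related discontinuations that section 8.1 says will be reported: if investigators follow different footnotes, those counts mix two rules.

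**Working it through.** No planned figure has to be reproduced; the check sets the rules side by side.

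**Inputs.** Start 60 mg (section 2.1; Appendix A, note j). Floor 45 mg (Table 12 footnote a; Table 15 footnote a). Floor 30 mg (Table 13 footnote b). Assumption: the levels are the three doses named in the visible text, 60, 45 and 30 mg.

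**Reductions available.**

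- Floor 45 mg: 60 → 45, one reduction; 45/60 = 75% of the starting dose.
- Floor 30 mg: 60 → 45 → 30, two reductions; 30/60 = 50% of the starting dose. The step from 45 to 30 mg is a cut of 1 − 30/45 = 33%.

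**A patient at 45 mg under each study-wide floor.**

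| Event at 45 mg | Floor 45 mg | Floor 30 mg |
|---|---|---|
| Second Grade 3 skin appearance, after a first that led to 45 mg | No lower level; copanlisib stopped | Interrupt, then 30 mg |
| First Grade 2 pneumonitis | Reduction does not apply; stopped if 45 mg is not tolerated | 30 mg after recovery |
| Grade 3 blood pressure during infusion, investigator wishes to reduce | No lower level | 30 mg, at discretion |
| Persistent glucose above 500 mg/dL despite optimal therapy, after at least one cycle | Stop | Stop condition not met; 30 mg still open |

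At 60 mg the two floors give the same action in every row, so the conflict affects only patients who have already been reduced once. The last row is conditional: it applies only if the glucose rule takes its lowest level from these footnotes and not from a list in section 6.2.

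**Floors that differ by toxicity.** On this reading a patient can go 60 → 45 → 30 mg for skin toxicity and then have a first Grade 2 pneumonitis. Table 15 calls for the next level down. Its exemption names only 45 mg, and no visible level lies below 30 mg, so the row as written has no dose to give.

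**The case against.** The strongest defence is that the floors are meant to differ by toxicity. Each fits the steps in its own table from 60 mg: one decrease and then a stop for pneumonitis, a one-level reduction for blood pressure, two decreases and then a stop for skin. Table 15 footnote a also forbids re-escalation, whereas section 6.3.1.1 allows it once glucose is controlled. At least that sentence must therefore be local to pneumonitis, and the sentence after it may be too. This is plausible. But no footnote says so, the wording is unqualified, and the case of a patient at 30 mg in Table 15 would still need an instruction. One can argue that stopping at 30 mg follows from stopping at 45 mg, and section 6.3 lets the physician depart from the algorithms in particular circumstances. Neither states the default.

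A reader might infer three stronger things that the documents do not support.

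- *That the glucose rule certainly yields opposite actions.* Its lowest level most naturally refers to the study's dose-level list. Section 6.2 contains a figure not shown, and Tables 1 to 4 are absent from the public copy, so the list may settle the matter.
- *That the plan leaves the dose levels undefined.* The same missing material rules this out. A list in section 6.2 could show which footnote is right, but it could not make unqualified floors of 45 and 30 mg both right.
- *That other rules prove 30 mg correct.* The note to Tables 5 to 8, "Patients requiring >2 dose reductions should go off protocol therapy", is a cap, and a cap that is never reached contradicts nothing. With re-escalation it could even be reached under a 45 mg floor. Section 6.3.3, "copanlisib may be resumed at the same dose level or at one or more dose levels lower", is discretionary. Neither states a floor.

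**Conclusion.** The footnotes conflict as worded, and the conflict is in visible operative text, so missing pages do not explain it. For a patient at 45 mg who needs less, the protocol gives both a stop and a reduction to 30 mg. Which value is intended cannot be determined from the public copy. The glucose rule is affected only if section 6.2 does not define its lowest level.

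This is a minor point, worth correcting. The size in dose terms is one reduction against two (75% against 50% of the starting dose), assuming levels of 60, 45 and 30 mg. The number of patients affected is not given and is probably small. Section 6.5 calls hyperglycemia very common with copanlisib, but the frequency above 500 mg/dL is not stated. The DLT definition, ORR analysis and sample size are not touched; the effect is on dosing conduct and on the counts of reductions and discontinuations.

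**What to change.** Align the three footnotes to the dose levels in section 6.2. Which edit applies depends on what that section lists.

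- **Levels 60/45/30 mg with one study-wide floor:** change 45 mg to 30 mg in Table 12 footnote a and throughout Table 15 footnote a, including its exemption from the reduction.
- **Floor 45 mg:** change 30 mg to 45 mg in Table 13 footnote b. Its existing discontinuation wording then covers the second Grade 3 skin appearance, so no table row has to change.
- **Floors meant to differ by toxicity:** add *for this toxicity* to each of the three footnotes, and state in Table 15 that a patient already at or below 45 mg is discontinued.

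In every case, write the mg value into the stop rule in section 6.3.1.1.

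The cost is between one and three footnotes, plus one sentence in section 6.3.1.1 and, for toxicity-specific floors, one statement in Table 15. Data collection and analysis do not change.
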